10.7 Report

After the data of all subjects were completely collected (within one year after the operation), a clinical study report would be compiled and submitted to NMPA for review as material supporting the extension of product registration.

11 Research Management and Administration

11.1 Responsibilities of investigators and the sponsor

11.1.1 Responsibilities of investigators

An investigator should ensure that all the work and services herein or incidental matters of all the work and services herein were implemented in accordance with the highest standards of medical and clinical study practice. An investigator should perform his/her duties according to all applicable laws and regulations. An investigator should provide a copy of the current study proposal to all assistant investigators or research staff of other research centers in charge of research implementation, and ensure all research staff are qualified, trained, and competent.

An investigator should submit the progress report, the safety report required by local regulations or national regulatory requirements, and study completion notice to the EC within the specified time limit.

11.1.2 Responsibilities of the sponsor

The sponsor should be solely responsible for the implementation of this study. The sponsors should ensure compliance with all applicable regulations and guidelines during this study.

The sponsor should properly monitor clinical study centers, obtain subjects' informed consent, provided quality data in compliance with regulations, notify investigators, ECs, and regulatory authorities of AEs, revocation of ethical approval, a list of current investigators (if necessary), and relevant safety issues, in accordance with international and local guidelines, and describe proposal deviation, as appropriate. The sponsor should write the safety report, the progress report, and the final clinical study report.

11.2 Assessment, initiation, monitoring, and close of visits

11.2.1 Assessment visits

The main requirements for which a research center and an investigator are selected and continue to

participate in this study include: They have sufficient experience in relevant research areas and all research operations, and adhere to safety commitments and the study proposal. The number of subjects should also be consistent with what is specified in the study proposal. The sponsor and its designated personnel should select qualified investigators, obtain a copy of signed research agreement from the latter, and provide the latter with the information necessary to implement this study, including any amendment or update to the research information specific to this study.

11.2.2 Initiation visits

At the beginning of this study, the monitor designated by the sponsor would visit research centers to confirm that all investigators personnel and research-related items were in place. The monitor would offer research-related training to investigators, including study proposals, informed consent procedures (if applicable), complaint of adverse events and research-related devices, completion of CRF, maintenance of research documents, responsibility of immediate notification to the sponsor of investigator changes, monitoring process, and GCP. During the initiation of visits, all preparations for subjects enrolled should be carried out.

11.2.3 Monitoring visits

At all research centers, the monitoring of this study should be carried out by the sponsor or personnel designated by the sponsor. Monitoring should ensure:

- Rights and health of subjects were protected;
- This study was conducted in accordance with all applicable regulations and guidelines;
- The study proposal and corresponding amendments were complied with;
- The accuracy of data recorded should be confirmed by verifying source documents.

Throughout the clinical study period, all effective research centers should be regularly monitored and visited to ensure that investigators fulfilled their obligations. These visits were to ensure that the research centers met requirements for facilities, follow the study proposal and all amendments, informed their ECs of changes to the proposal as required, maintain complete records, report to the sponsor and their ECs appropriately and in a timely manner, and that investigators were implementing all agreed matters.

11.2.4 Closing visiting of research centers

At the completion of the clinical study (Data were completely collected from all subjects enrolled. All CRFs were completed. And all data queries were resolved), the sponsor or designated personnel should inform research centers to end this study and close their visit to the centers.

At the last visit to research centers, all unused research materials should be collected and returned to the sponsor or destroyed at research centers. The monitor and investigator should ensure that the investigator folder and other research-related materials were up-to-date and complete, and that all outstanding issues of previous visits were resolved. During this visit, others issues to be reviewed included: storage of research materials, possibility of audit of research centers, open policies, and notice to ECs about the end of this study.

If a research center failed to enroll any subject for any reason, and the sponsor decided that the research center should stop further participation in this study, before the end of this clinical study, the last visit to the research center could be planned. In this case, the sponsor should instruct investigators to

complete the notification to the EC of the participation of the research center in this study and prepare the final documents required by the sponsor.

11.3 Documents required

Before enrolling subjects, at least the following documents should be submitted to the sponsor or designated personnel:

- The confidentiality agreement;
- Signed signature page of the study proposal;
- CVs of primary investigators and assistant investigators recently signed and dated; The CVs should clearly describe the qualifications and experience of research personnel;
- A copy of the written approval of the study proposal by ECs (including version number and date) and informed consent (including version and date) (if applicable);
- A list of current EC members, including name, title, occupation, and name of any organization of each member;
- Signed research contract.

11.3.1 Source documents

Regulations state that investigator should maintain the information in subjects' medical records (i.e., source documents). Such information could verify the data collected in CRFs. In order to comply with these regulatory requirements, the following information should be stored and available upon request by the monitor and/or inspectors of regulators:

- Information on medical history/physical condition of a subject that could prove the subject met the inclusion criteria of this study before participating in this study;
- Records on the informed consent process (if applicable);
- Description of implantation;
- All exam results and follow-up information;
- Dated and signed exam reports (e.g., X-ray);
- Description of an adverse event (description, severity, date, and duration of the adverse event, correlation with a research-related device, prognosis and treatment of the adverse event, and concomitant medication);
- Condition of a subject at the completion of or withdrawal from this study.

Source documents of a subject should include at least but not be limited to the above information.

11.3.2 Source data verification (SDV)

During visits, the monitor should check all the following key items in accordance with CRF entries of 100% of the subjects: all inclusion/exclusion criteria, the ICF (if applicable), demographic information of a subject, all events that met the criteria of reporting of adverse events (the inducing factor that

indicated the occurrence of an event), safety and efficacy endpoints, use of devices, re-operation, and all device failure/complaint reports. The monitor should check the other data of 50% of the subjects. For complete and details of verification of source data, please refer to the monitoring plan.

During a visit by the monitor, a research coordinator and/or an investigator should be present. The research coordinator or the investigator should ensure that the monitor could review source documents and provide the latter with an appropriate environment to review relevant documents. All inconsistencies should be identified and discussed with the investigator or designated personnel for resolution.

11.3.3 Case Record Form (CRF)

The CRF of each subject should be completed by an authorized investigator or another authorized personnel of research center. All the data on subjects required must be collected in CRFs. CRFs could not be used as a source document. The monitor should check completed CRFs at a research center to confirm the accuracy of the data collected in CRFs. All corrections to CRFs should be carried out by an authorized investigator or another authorized personnel of research center. to CRFs should be carried out by authorized investigator or other authorized personnel of the research center. The investigator /assistant investigator must sign and date at a specific part of CRF to prove that he/she had reviewed the data and ensured the data were complete and accurate.

A investigator should complete CRFs as soon as possible after a subject was screened or relevant information was collected. This would facilitate timely monitoring visits.

11.3.4 Archive and data retention

After being informed of the end of all research, a investigator should keep all research records, reports, and source documents supporting the completion of CRFs for at least 10 years and could continue to keep the data in line with the local and international guidelines specified in the clinical study agreement.

Investigators should be able to provide the document records at the request of regulators and the sponsor (designated personnel). Before the transfer of the documents, the sponsor or designated personnel must approve in writing the filing or transfer of the documents so as to relocate the documents. Investigators must notify the sponsor in writing of the location of the transfer and duration and procedures of reviewing the documents. Before destroying any records and reports related to this study, an investigator must contact the sponsor or designated personnel to confirm that the records and reports were no longer to be retained.

If an investigator no longer shouldered the main responsibility of storage of research records due to retirement, relocation, or other reasons, the investigator must transfer in writing the right of storage to the sponsor or designate personnel and indicate the name and address of the person with the primary responsibility.

11.3.5 Audit and inspection

In the case of an audit initiated by the sponsor (or its designated personnel), or a regulator, an investigator should ensure that auditors and inspectors had access to the original medical records during their audit or inspection, and provide all necessary information. In the case of an audit initiated by a regulator, an investigator should notify the sponsor immediately.

11.4 Data Collection and Management Responsibilities

Data collection is the responsibility of the clinical trial staff at the site under the supervision of the site Investigator. The Investigator is responsible for ensuring the accuracy, completeness, legibility, and timeliness of the data reported.

The recruitment of the study centers and the extraction of data from patients' medical records will be closely monitored to reach the proposed sample sizes. The study investigators will be asked to extract the data from the medical records of all patients implanted with Hakim programmable shunt system for the study in their respective centers. Integra Clinical Operations will follow up with the centers during the data collection process when appropriate to ensure a rapid completion of the data collection process.

Hardcopies of the study visit CRFs will be provided for use to collect data for each subject enrolled in the study. Data recorded in the CRFs derived from any source documents should be consistent with the data recorded on those source documents.

Clinical data (including AEs), concomitant medications, and expected adverse reactions data) and clinical laboratory data will be entered into Microsoft Access Database by Sponsor by double data entry. The data will be reviewed and validated. Queries for any missing, inconsistent or illogical data points will be forwarded to the research center for resolution. After all data queries are resolved, the data will be transferred to a biostatistician for analysis.

12 Ethical and Regulatory Requirements

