11.3.3 Case Record Form (CRF)	19
11.3.4 Archive and data retention.....	19
11.3.5 Audit and inspection.....	19
12 Ethical and Regulatory Requirements	20
12.1 Ethics Committee	20
12.2 Informed consent	20
12.3 Subject confidentiality.....	21
12.4 Revision of the study proposal	21
12.5 Proposal deviation.....	21
13 Publication Policies.....	21
14 Devices.....	22
14.1 Count of research-related devices	22
14.2 Return of research-related devices	22

Proposal No.: C-BSEAL-001

Date of proposal: V1.0/2019-11-18

14.3 Complaint about devices	22
14.3.1 Complaint about devices	22
References	23
Table 1: Product Specifications and Models.....	6

Summary of the Proposal

Research Topic:	A Multi-center, Retrospective Registry Study on the Safety of Bactiseal Catheterization
Research Purpose:	This study aimed to continue to evaluate safety information from subjects implanted with a catheter (trade name: Bactiseal) produced by Codman & Shurtleff, Inc. of the United States. Device safety would be assessed based on all the adverse events that occurred within one year after the subjects implanted the catheter.
No. of Subjects:	50
No. of Research Centers:	3 research centers
Research Design:	
This study was designed to be single arm, multi-center, and retrospective.
 
A total of 50 patients would be retrospectively enrolled. Information would be collected on adverse events of subjects enrolled within one year after the implantation of the Bactiseal Catheter from August 07, 2018 to January 31, 2021.
 
The following information would be collected from subjects' medical records or hospitals' databases (if any):
 
 1. General condition of the subjects 2. Intraoperative condition and catheter implantation 3. Information on the shunt product 4. Adverse events of subjects within one year after the operation and classification of the adverse events 5. Relevant examinations in case of postoperative infection 6. Other adverse event-related information (except anticipated adverse events)
Research Duration:	2020-

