1.2 Research-related devices

Devices verified in this study were catheters (trade name: Bactiseal) manufactured by Codman & Shurtleff, Inc., U.S.A. Its registration number is G.J20183132246. Please refer to the table below for the product specifications and models in this study.

Table 1: Product Specifications and Models

Model	Description	Inner diameter (mm)	Outer diameter (mm)
823072	Ventricle and abdominal catheter	1.4/1.0	2.7/2.2
823073	Ventricle catheter	1.4	2.7
823074	Abdominal catheter	1.0	2.2

2. Benefits/Risks

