3.2 Purpose

This study aimed to collect safety information from subjects implanted with a catheter (trade name: Bactiseal) produced by Codman & Shurtleff, Inc. of the United States. Device safety would be assessed based on all the adverse events that occurred within one year after the subjects were implanted with the catheter.

4. Research Design

This study was designed to be single arm, multi-center, and retrospective.

This is continued access study to enroll additional 50 new subjects, with total combined 150 subjects. The historical study is DPS-201501.

It would collect information on adverse events of subjects enrolled within one year after the implantation of Bactiseal Catheter from August 07, 2018 to August 31, 2019, through case review or hospital database (if any).

The following information would be collected from subjects' medical records:

1. General condition of the subjects
2. Intraoperative condition and catheter implantation
3. Information on the shunt product
4. Adverse events of subjects within one year after the operation and classification of the adverse events
5. Relevant examinations in case of postoperative infection
6. Other adverse event-related information (except anticipated adverse events)

Information on adverse events would be collected. And the safety of clinical application of the product would be assessed.

5. Endpoint

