6.1 Selection of subjects

Subjects who received a hydrocephalus shunt operation between August 07, 2018 to August 31, 2019 and met the inclusion criteria were enrolled. As this was a retrospective study, it would apply for the exemption of informed consent from the Ethics Committee of a center. For the centers which did not exempt informed consent, the informed consent process would be completed prior to the start of data collection, either by telephone or by anyway approved by the Ethics Committees.

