6.2 Inclusion criteria

Subjects who met all of the following inclusion criteria would be enrolled:

1. The informed consent was exempted by the Ethics Committee of a research center. Or a subject or his/her legal representative signed the informed consent form (ICF) prior to the enrollment;
2. A subject had an indication suitable to use Bactiseal Catheter;
3. A subject received hydrocephalus shunt at least one year ago.

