10.4 Criteria of qualification/disqualification of the trial results

This study aimed to collect post-marketing safety data on the Chinese population implanted Bactiseal Catheter, according to product registration requirements. It described the occurrence, type, severity, frequency of all AEs occurring during the research, as well as the correlation between AEs and the product. Hence, criteria of qualification/disqualification were not applicable.

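### Section 11.4 sends sites to Hakim shunt patients, while the study is defined by Bactiseal implantation and no eligibility criterion expressly requires that Bactiseal was implanted

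*Combined protocol and SAP*

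**What the plan says.** The extraction instruction is in Section 11.4, where investigators are to "extract the data from the medical records of all patients implanted with Hakim programmable shunt system for the study in their respective centers".

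The rest of the plan names a different product:

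- Section 1.2: "Devices verified in this study were catheters (trade name: Bactiseal"; Table 1 lists models 823072, 823073 and 823074.
- Section 3.2: "This study aimed to collect safety information from subjects implanted with a catheter (trade name: Bactiseal".
- Summary, Research Design: the data are "adverse events of subjects enrolled within one year after the implantation of the Bactiseal Catheter". Section 4 says the same of "subjects enrolled within one year after the implantation of Bactiseal Catheter from August 07, 2018 to August 31, 2019".
- Section 10.4: "This study aimed to collect post-marketing safety data on the Chinese population implanted Bactiseal Catheter".

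The rules that decide who is in the cohort are looser. Section 6.1 reads "Subjects who received a hydrocephalus shunt operation between August 07, 2018 to August 31, 2019 and met the inclusion criteria were enrolled", with no device named. In 6.2, inclusion 1 concerns consent or its waiver, inclusion 2 is "A subject had an indication suitable to use Bactiseal Catheter", and inclusion 3 asks for a hydrocephalus shunt at least a year earlier. Section 7.1.3 enrols anyone who meets these criteria and no exclusion, subject to consent where it was not waived. Section 10.6 makes the per-protocol set the primary analysis population and defines it by the inclusion and exclusion criteria alone.

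**The concern.** Section 11.4 is an operative sentence. Screening in 7.1.1 says only that records are reviewed for eligible subjects. The sentence in 11.4 is the one that tells sites to pull all patients with a named device, so it sets the frame from which the cohort is drawn. It names a product that is not the study device.

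Normally the eligibility criteria would correct such a slip. Here none of them says outright that the study catheter must have been implanted, so the slip is not clearly caught where the cohort and the primary population are defined. The denominator of the one-year infection-free rate is at stake. According to 10.7, the report goes to the regulator in support of extending the product registration, so the cohort should be unambiguously patients with that product.

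**Working it through.** The point is textual and the plan states no figure to reproduce. The check takes three kinds of patient through the rules in order.

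**Do the two products identify the same patients?** The documents do not say. They do not describe the Hakim system or state that it was always used with Bactiseal. Section 7.3 records the pressure regulating valve separately from the ventricular and distal catheters, so a Hakim label does not settle which catheter a patient received.

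**Patient A: Hakim system, no Bactiseal catheter.**
- 11.4: record extracted.
- Inclusion 1: met if consent was waived or given.
- Inclusion 2: can be met, because it concerns the indication. Section 3.1 describes that only as use within a shunt system for hydrocephalus.
- Inclusion 3: met by any hydrocephalus shunt of sufficient age.
- Exclusion 2 (allergy to the product's components, including rifampicin and clindamycin): presupposes Bactiseal but removes only allergic patients.
- Exclusion 4: removes patients given another system simultaneously. It is unclear whether that covers a system placed instead of Bactiseal. The Summary and 6.3 word it differently.
- Exclusions 1, 3, 5 and 6: concern indication, infection, contraindication and bleeding, not which catheter was used.
- 7.1.3 and 10.6: no stated inclusion criterion is breached. Unless exclusion 4 is read broadly, A is enrolled and enters the per-protocol set.

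**Patient B: Bactiseal catheter, no Hakim system.**
- Can satisfy every criterion and belongs to the intended population.
- 11.4 does not ask for this record, so B may never be extracted.

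**Patient C: both products.**
- Extracted and intended, but the Summary's exclusion 4 bars a shunt system different from Bactiseal. Depending on how a Hakim system is classed, that wording could be read to remove C. The passages need reconciling.

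**What would the safeguards catch?**
- Section 7.3 records type, number and batch of the catheters, 11.3.2 verifies device use for 100% of subjects, and 10.6 lists all data. Together these would probably reveal A.
- Having revealed A, the plan gives no express criterion on which to remove A. Section 12.5 classes breaches of the inclusion or exclusion criteria as primary violations, but A breaches no stated inclusion criterion.
- The source data check works from the case record forms of subjects already extracted, so it would not reveal B.

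**Can the size be worked out?** No. It needs the number of patients at the three centres with each product and with both, and the documents give none of these. If every Hakim patient also had Bactiseal, the number of A patients is zero. If every Bactiseal patient also had a Hakim system, the number of B patients is zero.

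**The case against.** The strongest reply is that nobody reading the whole protocol would mistake the study device. The purpose, device table, design and Section 10.4 all say Bactiseal. Section 11.4 is a data-management paragraph, while enrolment is governed by 7.1.3, and the Hakim name reads as a stray product name. Sites are trained on the protocol (11.2.2), device use is checked for every subject, and 11.4 itself sends queries back to the centre before data reach the biostatistician. In a record review with no intervention, a late correction costs little.

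Much of this stands. The intent is clear and wrongly extracted patients would probably be noticed. It does not answer the patients who are never extracted, and it does not supply a written rule for removing those who should not be there.

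Three stronger readings are tempting, and the documents do not support them:

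- *That the criteria are silent on Bactiseal.* They are not. Inclusion 2 and exclusion 4 name it, and exclusion 2 describes it by its ingredients. What is missing is an express requirement that it was implanted.
- *That the infection rate is biased by a calculable amount.* That would need an assumed share of patients without Bactiseal, for which there is no basis. It would also mean setting the pooled 7.1% for non-antibiotic catheters (1.1) against the 4.3% planning rate (10.3), which was deliberately set above the 3.2% literature estimate. The 7.1% includes a trial with a median follow-up of 22 months, so it is not a clean one-year figure.
- *That removing wrong-device patients would widen the planned 3.4-point margin.* That assumes they are not replaced. The no-replacement rule in 9.2 covers only subjects who end the study early, and 11.4 says extraction is monitored so that the proposed sample sizes are reached.

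**Conclusion.** The point holds as a contradiction between an operative instruction and the defined study population, together with eligibility wording that does not expressly resolve it. Taken literally, 11.4 can omit Bactiseal patients without a Hakim system and admit Hakim patients without Bactiseal. The existing checks would probably find the latter but not the former.

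No effect size is claimed. The number of patients affected is unknown and may be zero. The conclusion assumes only that the two products do not necessarily identify the same patients, and nothing in the documents rules that out. Because the intent is clear and device data are recorded and verified, this should be fixed but does not undermine the study.

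**What to change.** 1. In 11.4, replace the Hakim product name with the Bactiseal Catheter, Table 1 models 823072, 823073 and 823074.
2. In the Summary and 6.2, add an inclusion criterion that a Table 1 Bactiseal catheter was implanted at the index operation, confirmed from the 7.3 device record. Sections 7.1.3 and 10.6 then inherit it. State whether a single Bactiseal component is enough. Table 1 lists ventricular and abdominal catheters separately as well as together, and 7.3 also provides for lumbar cistern and atrial catheters, which Table 1 does not list.
3. Reconcile the two wordings of exclusion 4 (Summary and 6.3) with the new criterion and with each other.

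The cost is a wording amendment. No new data are needed, since catheter type, number and batch are already collected and device use is already verified for all subjects. It is not administratively free: 12.1 bars changes without ethics committee consent, and under 12.4 a new inclusion criterion may count as a major amendment needing approval at each centre.
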